8.0 ADMINISTRATIVE AND REGULATORY DETAILS

8.1 Data Reporting

RedCap will be the electronic data capture (EDC) system utilized for data collection. Clinical data will be entered on electronic, study-specific case report forms (eCRFs) built and maintained in the eResearch application. All data entries to CRFs must be supported by a clinical source document. No direct entry of patient data to the CRF is permitted.

8.2 Continuing Review and Final Reports

An annual progress report (continuing review) will be submitted to the FDA annually for the duration of the study and to the IRB of record at the interval it determines, but at least annually. Continuing review reports to the FDA will comply with Title 21, Part 312.33 of the Code of Federal Regulations.

8.3 Protocol Modifications and Amendments

All modifications or amendments to the protocol or informed consent document must be approved by the Principal Investigator and submitted to the IRB for review and approval. All modifications and amendments will be documented with a new version number and date. All changes to the informed consent document will include the date of the revision on the form.

No changes will be implemented until IRB approval is obtained except when a potential threat to patient safety exists.

The IRB will be notified of any significant deviations from the approved protocol. Documentation of all IRB correspondence will be maintained in a central regulatory file.

8.4 Record Retention

According to 21 CFR 312.62(c), the investigator shall retain required records for a period of 2 years following the date a marketing application is approved for the drug for the indication for which it is being investigated. If no application is to be filed or if the application is not approved for such indication, the investigator shall retain these records until 2 years after the investigation is discontinued (IND is withdrawn) and the FDA is notified.

The investigator must retain protocols, amendments, IRB/IBC approvals, copies of the Form FDA 1572, completed, signed, dated consent forms, patient source documents, case report forms, quality monitoring reports, drug accountability records and all documents of any nature regarding the study or patients enrolled. All records will be maintained under restricted access by the Clinical Trials Department at Providence Portland Medical Center while the study remains active. Records may be placed in long-term storage after the study is completed. The location of long-term storage will be secure and easily accessed for regulatory purposes.

8.5 Study Monitoring

Clinical research staff members who have completed specialized training in study monitoring procedures and human subjects' protections perform study monitoring activities (Quality Control Reviews). Individuals who perform study monitoring activities do not report to Principal Investigators or research scientists and may not monitor studies for which they have direct responsibility.

Study monitoring activities are conducted regularly and include (but are not limited to) review and verification of the following:

- Eligibility
- Informed Consent process
- Adherence to protocol treatment plan
- Case Report Forms (CRFs)
- Source Documentation
- Adverse Events
- Regulatory Reporting

Results of study monitoring activities will be reported to applicable study personnel, the Administrative Director of Clinical Research and Quality Assurance. Quality Assurance (QA) personnel review study monitoring reports and, if necessary, determine follow-up actions to resolve significant findings. QA has the authority to request immediate corrective action if significant patient safety issues are identified.

QA will track and trend results from study monitoring reports as well as associated corrective and preventive actions. A QA summary report will be provided to the IRB at the time of continuing review.

QA personnel do not have a direct reporting relationship to the Principal Investigator and are not responsible for enrollment or coordination of care for study participants.

External sites

Monitoring will occur at intervals stipulated in the monitoring plan for the study. Monitoring may be performed on-site or remotely. Monitoring will include: review regulatory documentation, CRFs, source documentation, and investigational product storage, preparation, and accountability. The CRFs will be reviewed for completeness and accuracy compared to the source documents.

8.6 Quality Assurance Plan

The Providence Health System Quality Assurance (QA) plan for cancer clinical trials comprises Standard Operating Procedures (SOPs) that require ongoing review of activities associated with all investigator-initiated trials including protocol compliance, accuracy of data and safety of participants.

Quality Assurance (QA) personnel review study monitoring reports and if necessary, determine followup actions to resolve significant findings. QA has the authority to request immediate corrective action if significant patient safety issues are identified.

QA will track and trend results from study monitoring reports as well as associated corrective and preventive actions. A QA summary report will be provided to the IRB at the time of continuing review.

QA personnel do not have a direct reporting relationship to the Principal Investigator and are not responsible for enrollment or coordination of care for study participants.

Confidential

All case report forms will undergo quality assurance review. All quality assurance reviews will include verification of the accuracy and integrity of data entered to case report forms. Incorrect data will be identified and corrected. The existence of adequate source documents for all data will be verified. A staff person not associated with patient care coordination, data completion or submission will review all annual reports.

8.7 Safety Monitoring Plan

Oversight of participant safety will include review of adverse events as well as study progress and outcomes.

Adverse events, outcomes, and recruitment and retention of patients will be reviewed on a weekly basis by the PI, research nurse, and data coordinator. Protocol deviations are reviewed monthly at the Cancer Research Meeting.

10.0 APPENDICES

Appendix 1: ECOG Performance Status

Grade	Description	
0	Normal activity. Fully active, able to carry on all pre-disease	
0	performance without restriction.	
	Symptoms, but ambulatory. Restricted in physically strenuous	
1	activity, but ambulatory and able to carry out work of a light or	
	sedentary nature (e.g., light housework, office work).	
	In bed <50% of the time. Ambulatory and capable of all self-care, but	
2	unable to carry out any work activities. Up and about more than 50%	
	of waking hours.	
3	In bed >50% of the time. Capable of only limited self-care, confined	
5	to bed or chair more than 50% of waking hours.	
4	100% bedridden. Completely disabled. Cannot carry on any self-care.	
4	Totally confined to bed or chair.	
5	Dead.	
* As published in Am. J. Clin. Oncol.: Oken, M.M., Creech, R.H., Tormey, D.C., Horton, J., Davis, T.E.,		
McFadden, E.T., Carbone, P.P.: Toxicity And Response Criteria Of The Eastern Cooperative Oncology		
Group. Am J Clin	Oncol 5:649-655, 1982. The Eastern Cooperative Oncology Group, Robert Comis	
M.D., Group Chair.		

Appendix 2: Clinical Laboratory Tests

- The tests detailed in Table 9 will be performed by the local laboratory.
- Protocol-specific requirements for inclusion or exclusion of participants are detailed in Section 5.1 of the protocol.
- Additional tests may be performed at any time during the study as determined necessary by the investigator or required by local regulations.

Laboratory	Parameters						
Assessments					-		
Hematology	Platelet Count		RBC Indices:		WBC count with		
	RBC Count		MCV		Differential:		
	Hemoglobin				Neutrophils		
	Hematocrit			Lymphc		hocytes	
				Monocytes			
				Eosinophils			
				Basophils			
Chemistry	BUN	Potass	ium	AST/SGOT		Total bilirubin (and	
						direct bilirubin, if	
						total bilirubin is	
						elevated above the	
						ULN)	
	Albumin	Bicarbonate		Chloride		Phosphorous	
	Creatinine		n	ALT (including LFT)/SGPT		Total Protein	
	Glucose [Indicate if	Calcium		Alkaline		Thyroid Funtion	
	fasting, or			phosphatase		Tests (LDH, Free	
	nonfasting]					T4, TSH)	
	INR or PT and						
	aPTT						
Routine	Specific gravity						
Urinalysis	• Specific gravity						
	• pH, glucose, protein, blood, ketones, nitrite, leukocyte esterase by dipstick						
	Microscopic examination (if blood or protein is abnormal)						
	• 24-hour urine collection for quantitative assessment of proteinuria may also be required						
	at screening to determine eligibility						
Pregnancy	Highly sensitive serum hCG pregnancy test (as needed for WOCBP)						
Testing							
Other Screening	• FSH (as needed in WOCBP only)						
Tests							
ALT=alanine aminot	ransferase; AST=aspartate	aminotra	ansferase; BUN=b	olood urea nitroger	n; FSH=f	follicle-stimulating	
hormone; hCG=human chorionic gonadotropin; MCH=mean corpuscular hemoglobin; MCV=mean corpuscular volume;							
RBC=red blood cell; SGOT=serum glutamic-oxaloacetic transaminase; SGPT=serum glutamic-pyruvic transaminase;							
ULN=upper limit of normal; WOCBP=women of childbearing potential; WONCBP=women of nonchildbearing potential							

Table 9 Protocol-required Safety Laboratory Assessments

The investigator (or medically qualified designee) must document their review of each laboratory safety report.

Protocol 2021000802 MISP 60931 Version Date: 30Jul2024

Appendix 3: Contraceptive Guidance and Pregnancy Testing

Woman of Childbearing Potential (WOCBP)

A woman is considered fertile following menarche and until becoming post-menopausal unless permanently sterile (see below)

Women in the following categories are not considered WOCBP:

- Premenarchal
- Premenopausal female with 1 of the following:
 - Documented hysterectomy
 - Documented bilateral salpingectomy
 - Documented bilateral oophorectomy

Note: Documentation can come from the site personnel's review of the participant's medical records, medical examination, or medical history interview.

- Postmenopausal female
 - A postmenopausal state is defined as no menses for 12 months without an alternative medical cause.
 - A high follicle stimulating hormone (FSH) level in the postmenopausal range may be used to confirm a postmenopausal state in women not using hormonal contraception or hormonal replacement therapy (HRT). However, in the absence of 12 months of amenorrhea, confirmation with two FSH measurements in the postmenopausal range is required.
 - Females on HRT and whose menopausal status is in doubt will be required to use one of the nonhormonal highly effective contraception methods if they wish to continue their HRT during the study. Otherwise, they must discontinue HRT to allow confirmation of postmenopausal status before study enrollment.

Contraception Requirements

Male Participants:

Male participants with female partners of childbearing potential are eligible to participate if they agree to one of the following during the protocol defined time frame in section 5.11:

- Be abstinent from penile-vaginal intercourse as their usual and preferred lifestyle (abstinent on a long term and persistent basis) and agree to remain abstinent
- Use a male condom plus partner use of a contraceptive method with a failure rate of <1% per year as described in Table 10 when having penile-vaginal intercourse with a woman of childbearing potential who is not currently pregnant.

• Note: Men with a pregnant or breastfeeding partner must agree to remain abstinent from penilevaginal intercourse or use a male condom during each episode of penile penetration.

Female Participants:

Female participants of childbearing potential are eligible to participate if they agree to use a highly effective (with a failure rate of <1% per year) method of contraception that has a low user dependency consistently and correctly as described in Table 10 during the protocol-defined time frame in Section 5.1.3.2.

Table 10 Highly Effective Contraceptive Methods That Have Low User Dependency

Highly Effective Methods That Have Low User Dependency Failure rate of <1% per year when used consistently and correctly.		
• Progestogen- only contraceptive implant ^{a, b}		
• Intrauterine hormone-releasing system (IUS) ^b		
• Intrauterine device (IUD)		
Bilateral tubal occlusion		
Vasectomized partner		
A vasectomized partner is a highly effective contraception method provided that the partner is sole male sexual partner of the WOCBP and the absence of sperm has been confirmed. If not, additional highly effective method of contraception should be used.		
Sexual abstinence		
Sexual abstinence is considered a highly effective method only if defined as refraining from heterosexual intercourse during the entire period of risk associated with the study treatment. The reliability of sexual abstinence needs to be evaluated in relation to the duration of the study and th preferred and usual lifestyle of the participant.		
Notes:		
Use should be consistent with local regulations regarding the use of contraceptive methods for participants of clinical studies.		
 a) If locally required, in accordance with Clinical Trial Facilitation Group (CTFG) guidelines, acceptable contraceptive implants are limited to those which inhibit ovulation. b) If hormonal contraception efficacy is potentially decreased due to interaction with study treatment, condoms must be used in addition to the hormonal contraception during the treatment period and for at least 120 days after the last dose of study treatment. 		

Pregnancy Testing

WOCBP should only be included after a negative highly sensitive serum pregnancy test.

Following initiation of treatment, pregnancy testing will be performed whenever an expected menstrual cycle is missed or when pregnancy is otherwise suspected; at the time points specified in the Schedule of Activities (Section 2.3), and as required locally.

Protocol 2021000802 MISP 60931 Version Date: 30Jul2024

Appendix 4: Description of the iRECIST Process for Assessment of Disease Progression

Assessment at Screening and Prior to RECIST 1.1 Progression

Until radiographic progression based on RECIST 1.1, there is no distinct iRECIST assessment.

Assessment and Decision at RECIST 1.1 Progression

In participants who show evidence of radiological PD by RECIST 1.1 the Investigator will decide whether to continue a participant on study treatment until repeat imaging 4 to 8 weeks later is obtained (using iRECIST for participant management (see Table 6 and Figures 1 and 2). This decision by the Investigator should be based on the participant's overall clinical condition.

Clinical stability is defined as the following:

- Absence of symptoms and signs indicating clinically significant progression of disease
- No decline in ECOG performance status
- No requirements for intensified management, including increased analgesia, radiation, or other palliative care

Any participant deemed clinically unstable should be discontinued from study treatment at site-assessed first radiologic evidence of PD and is not required to have repeat tumor imaging for confirmation of PD by iRECIST.

If the Investigator decides to continue treatment, the participant may continue to receive study treatment and the tumor assessment should be repeated 4 to 8 weeks later to confirm PD by iRECIST, per Investigator assessment.

Tumor flare may manifest as any factor causing radiographic progression per RECIST 1.1, including:

- Increase in the sum of diameters of target lesion(s) identified at baseline to $\ge 20\%$ and ≥ 5 mm from nadir
 - Please note: the iRECIST publication uses the terminology "sum of measurements", but "sum of diameters" will be used in this protocol, consistent with the original RECIST 1.1 terminology.
- Unequivocal progression of non-target lesion(s) identified at baseline
- Development of new lesion(s)

iRECIST defines new response categories, including iUPD (unconfirmed progressive disease) and iCPD (confirmed progressive disease). For purposes of iRECIST assessment, the first visit showing progression according to RECIST 1.1 will be assigned a visit (overall) response of iUPD, regardless of which factors caused the progression.
At this visit, target and non-target lesions identified at baseline by RECIST 1.1 will be assessed as usual.

New lesions will be classified as measurable or non-measurable, using the same size thresholds and rules as for baseline lesion assessment in RECIST 1.1. From measurable new lesions, up to 5 lesions total (up to 2 per organ), may be selected as New Lesions – Target. The sum of diameters of these lesions will be calculated and kept distinct from the sum of diameters for target lesions at baseline. All other new lesions will be followed qualitatively as New Lesions – Non-target.

Assessment at the Confirmatory Imaging

On the confirmatory imaging, the participant will be classified as progression confirmed (with an overall response of iCPD), or as showing persistent unconfirmed progression (with an overall response of iUPD), or as showing disease stability or response (iSD/iPR/iCR).

Confirmation of Progression

Progression is considered confirmed, and the overall response will be iCPD, if ANY of the following occurs:

- Any of the factors that were the basis for the initial iUPD show worsening
 - For target lesions, worsening is a further increase in the sum of diameters of ≥ 5 mm, compared to any prior iUPD time point
 - For non-target lesions, worsening is any significant growth in lesions overall, compared to a prior iUPD time point; this does not have to meet the "unequivocal" standard of RECIST 1.1
 - For new lesions, worsening is any of these:
 - An increase in the new lesion sum of diameters by ≥ 5 mm from a prior iUPD time point
 - Visible growth of new non-target lesions
 - The appearance of additional new lesions
- Any new factor appears that would have triggered PD by RECIST 1.1

Persistent iUPD

Progression is considered not confirmed, and the overall response remains iUPD, if:

- None of the progression-confirming factors identified above occurs AND
- The target lesion sum of diameters (initial target lesions) remains above the initial PD threshold (by RECIST 1.1)

Additional imaging for confirmation should be scheduled 4 to 8 weeks from the scan on which iUPD is seen. This may correspond to the next visit in the original visit schedule. The assessment of the

Confidential

subsequent confirmation scan proceeds in an identical manner, with possible outcomes of iCPD, iUPD, and iSD/iPR/iCR.

Resolution of iUPD

Progression is considered not confirmed, and the overall response becomes iSD/iPR/iCR, if:

- None of the progression-confirming factors identified above occurs, AND
- The target lesion sum of diameters (initial target lesions) is not above the initial PD threshold.

The response is classified as iSD or iPR (depending on the sum of diameters of the target lesions), or iCR if all lesions resolve.

In this case, the initial iUPD is considered to be pseudo-progression, and the level of suspicion for progression is "reset". This means that the next visit that shows radiographic progression, whenever it occurs, is again classified as iUPD by iRECIST, and the confirmation process is repeated before a response of iCPD can be assigned.

Management Following the Confirmatory Imaging

If repeat imaging does not confirm PD per iRECIST, as assessed by the Investigator, and the participant continues to be clinically stable, study treatment may continue and follow the regular imaging schedule. If PD is confirmed, participants will be discontinued from study treatment.

NOTE: If a participant has confirmed radiographic progression (iCPD) as defined above, but the participant is achieving a clinically meaningful benefit, an exception to continue study treatment may be considered. In this case, if study treatment is continued, tumor imaging should continue to be performed following the intervals as outlined in Section 6.

Detection of Progression at Visits After Pseudo-progression Resolves

After resolution of pseudo-progression (ie, achievement of iSD/iPR/iCR), iUPD is indicated by any of the following events:

- Target lesions
 - Sum of diameters reaches the PD threshold (≥ 20% and ≥ 5 mm increase from nadir) either for the first time, or after resolution of previous pseudo-progression. The nadir is always the smallest sum of diameters seen during the entire trial, either before or after an instance of pseudo-progression.
- Non-target lesions
 - If non-target lesions have never shown unequivocal progression, their doing so for the first time results in iUPD.

- If non-target lesions had shown previous unequivocal progression, and this progression has not resolved, iUPD results from any significant further growth of non-target lesions, taken as a whole.
- New lesions
 - New lesions appear for the first time
 - o Additional new lesions appear
 - Previously identified new target lesions show an increase of \geq 5 mm in the new lesion sum of diameters, from the nadir value of that sum
 - Previously identified non-target lesions show any significant growth

If any of the events above occur, the overall response for that visit is iUPD, and the iUPD evaluation process (see Assessment at the Confirmatory Imaging above) is repeated. Progression must be confirmed before iCPD can occur.

The decision process is identical to the iUPD confirmation process for the initial PD, except in one respect. If new lesions occurred at a prior instance of iUPD, and at the confirmatory scan the burden of new lesions has increased from its smallest value (for new target lesions, their sum of diameters is \geq 5 mm increased from its nadir), then iUPD cannot resolve to iSD or iPR. It will remain iUPD until either a decrease in the new lesion burden allows resolution to iSD or iPR, or until a confirmatory factor causes iCPD.

Additional details about iRECIST are provided in the iRECIST publication [28].

Appendix 5: Adverse Events: Definitions and Procedures for Recording, Evaluating, Follow-up, and Reporting

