3.2 Secondary Objective(s), Hypothesis(es), and Endpoint(s)

(1) **Objective**: To evaluate the objective response rate resulting from treatment with Lenvatinib + pembrolizumab.

Hypothesis: Treatment with Lenvatinib + pembrolizumab will result in an improved objective response rate as compared with previously reported therapies including pembrolizumab monotherapy, ipilimumab + nivolumab and tebentafusp.

Secondary Endpoint: Objective response rate (complete and partial responses assessed by iRECIST)

(2) **Objective**: To evaluate the effect of treatment with Lenvatinib + pembrolizumab on overall survival.

Hypothesis: Treatment with Lenvatinib + pembrolizumab will result in improved overall survival as compared with previously reported therapies including pembrolizumab monotherapy, ipilimumab + nivolumab and tebentafusp.

Secondary Endpoint: Overall survival, defined as the time from enrollment to death (resulting from any cause).

(3) **Objective**: To evaluate the safety and tolerability of treatment with Lenvatinib + pembrolizumab in patients with metastatic uveal melanoma.

Hypothesis: Treatment with Lenvatinib + pembrolizumab will demonstrate an acceptable toxicity profile in patients with metastatic uveal melanoma.

Secondary Endpoint:

• Adverse events (per CTCAE v5.0)

• Frequency of treatment interruption, dose reduction, and treatment discontinuation due to treatment related adverse events (TRAE).

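### For a first unconfirmed progression caused only by new or non-target lesions, Appendix 4 assigns iSD or iPR when those lesions merely persist, so an iRECIST response rate can include patients already progressed by RECIST 1.1

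*Combined protocol and SAP*

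**What the plan says.** Appendix 4 recognises three routes to radiographic progression: growth of the baseline target sum, unequivocal non-target progression, and new lesions. The first visit showing any of them "will be assigned a visit (overall) response of iUPD, regardless of which factors caused the progression".

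The confirmatory scan gives iCPD if a triggering factor worsens or a new RECIST 1.1 progression factor appears. For new lesions, worsening means at least 5 mm growth in their sum, visible growth of new non-target lesions, or further new lesions. For non-target lesions it means significant growth.

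If none of this happens, two outcomes remain. *Persistent iUPD* and *Resolution of iUPD* share the first condition: "None of the progression-confirming factors identified above occurs AND". They differ only in the second. For persistence it is "The target lesion sum of diameters (initial target lesions) remains above the initial PD threshold (by RECIST 1.1"; for resolution it is "The target lesion sum of diameters (initial target lesions) is not above the initial PD threshold". On resolution, "The response is classified as iSD or iPR (depending on the sum of diameters of the target lesions), or iCR if all lesions resolve". The episode is then called pseudo-progression, and the next progression starts again as iUPD.

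For later episodes only, Appendix 4 adds that if new lesions occurred before and their burden is above its smallest value, "then iUPD cannot resolve to iSD or iPR".

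Section 3.2 defines the endpoint as "Objective response rate (complete and partial responses assessed by iRECIST". Section 6.1.4.4 makes RECIST 1.1 the primary measure of tumor response and of the progression date. Section 7.2 stops enrollment after 15 evaluable subjects if ORR is below 20% (3 of 15) or median PFS is below 6 months. It does not say which criterion the ORR count uses.

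**The concern.** An iUPD should count as resolved because whatever caused it has gone away or shrunk. The rule does not ask that of new or non-target lesions; it asks only that they have not worsened. If the iUPD came from such lesions alone, the target sum may never have crossed the progression threshold, so the one condition that would hold the patient at iUPD cannot be met. A patient with persisting new metastases and a partial-response-level fall in the baseline targets is then classed as iPR.

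For ORR the effect goes one way: it can add responders and cannot remove any. ORR is a secondary endpoint, the only endpoint with a power table, and one of the two interim stopping criteria. The comparator rate is 10%, so at 15 or 30 patients one or two such cases are visible.

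**Working it through.** **1. The rule for a first iUPD whose triggering lesions do not worsen** (Appendix 4)

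| Cause of first iUPD | Target sum above threshold | Target sum not above threshold |
|---|---|---|
| Target growth | iUPD | iSD/iPR; the trigger has regressed |
| New lesions only | outside this case | iSD/iPR; the trigger may be unchanged |
| Non-target only | outside this case | iSD/iPR; the trigger may be unchanged |

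In the last two rows the target sum was not above the threshold when iUPD was assigned. If it later rose above it, that would be a new progression factor and would give iCPD. Persistent iUPD is therefore unreachable.

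**2. Illustration** (lesion sizes assumed)

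- Baseline: targets 60 mm.
- Week 9: targets 40 mm, one new measurable 15 mm lesion followed as a new target lesion. The target change is (40 − 60)/60 = −33%, taken here as partial-response level because the documents do not restate that cut-off. The visit is iUPD.
- Week 14 (inside the 4 to 8 week window): targets 40 mm, new lesion still 15 mm. The progression threshold from the 40 mm nadir needs both +20% (48 mm) and +5 mm (45 mm), so 48 mm. Since 40 < 48 and nothing has worsened, the visit is iPR.
- Week 18, same picture: at least 4 weeks later, so the iPR has the repeat imaging that Section 6.1.4.2 asks for.

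By RECIST 1.1 this patient progressed at week 9.

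**3. Two places where the appendix shows the gap itself.** Its rules for visits after pseudo-progression resolves provide for earlier non-target progression that has still not resolved. It then presents the new-lesion check as the single difference between later episodes and the first. The first episode therefore has no such check, and non-target lesions never have one.

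**4. The plan's own figures.** With n = 30, p0 = 0.10 and one-sided 0.05, power = Φ{[(p1 − p0) − 1.645·√(p0(1 − p0)/n)] / √(p1(1 − p1)/n)}. For p1 = 0.20: (0.10 − 1.645 × 0.0548)/0.0730 = 0.136, and Φ = 0.554. For 0.25 and 0.30 the results are 0.776 and 0.906. The plan states 0.55, 0.78 and 0.91, so the table reproduces. It does not depend on this point.

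**5. Size.** One patient is 1/15 = 6.7 points at the interim and 1/30 = 3.3 points at the end. On the ORR criterion, 2/15 = 13% stops and 3/15 = 20% does not.

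As a sensitivity range, assume a true ORR of 10% plus an extra share of patients counted as iPR by this route. P(X ≥ 3) = 1 − Σ(k = 0 to 2) C(15,k)·p^k·(1 − p)^(15−k), and likewise for 7 of 30, the smallest count with exact one-sided error under 0.05 (0.026; 6 of 30 gives 0.073).

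| Extra points (assumed) | P(≥3 of 15) | P(≥7 of 30) |
|---|---|---|
| 0 | 0.18 | 0.026 |
| 3.3 | 0.32 | 0.095 |
| 6.7 | 0.47 | 0.225 |

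**The case against.** The strongest reply is that Section 6.1.4.4 gives response and progression date to RECIST 1.1, and that Appendix 4 presents iRECIST as a tool for participant management. If RECIST 1.1 governs ORR, the first progression stands and the rule has no effect on the endpoint. That is correct as a conditional, but Section 3.2 names iRECIST for ORR and nothing in the plan settles the conflict.

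The route is also narrow. It needs a partial-response-level fall in the targets together with new or non-target progression, clinical stability, continued treatment, no qualifying growth, and a repeat scan. A new target lesion that keeps growing would reach 5 mm above its nadir and return to iUPD. These points limit the frequency but do not close the gap.

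It can also be said that the rule is explicit and not an oversight. Whether it departs from the cited iRECIST publication cannot be judged from these documents, and the point does not rest on that.

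Four stronger readings are tempting and are not supported:
- That resolution looks at the target sum alone. Worsening of new and non-target lesions is checked too; the gap concerns lesions that persist without it.
- That every relabelled patient inflates ORR. iSD is not a response; only a confirmed iPR counts.
- That the reset erases a progression date. The text resets the level of suspicion and says nothing about dates. Section 3.1 defines PFS by first documented progression without naming iRECIST.
- That one such patient keeps the trial open. Median PFS below 6 months stops enrollment independently.

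**Conclusion.** The point holds for a first iUPD caused only by new lesions or non-target progression, with the baseline target sum not above the threshold. Persistence without qualifying worsening is then labelled iSD or iPR. Where ORR follows iRECIST, a confirmed iPR of this kind counts as a response in a patient who has progressed by RECIST 1.1. Later episodes are partly protected for new lesions and not for non-target lesions.

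The size is 6.7 points per patient at n=15 and 3.3 at n=30. The probabilities in the table rest on an assumed share of affected patients, because the documents give none; they show sensitivity and are not an estimate. Section 7 also disclaims formal comparisons, so the 7-of-30 column is only a yardstick. The primary PFS endpoint is not shown to be affected.

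**What to change.** For endpoint derivation only, with site treatment decisions left to the existing text:

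1. Amend *Persistent iUPD* and *Resolution of iUPD* so that, at the first episode as well as later ones, a time point stays iUPD and is not eligible as iPR or iCR while the new or non-target lesions that triggered it persist without regression. A decrease in new-lesion burden, as Appendix 4 already accepts for later episodes, or resolution of the non-target progression, allows iSD or iPR. Requiring new lesions to disappear would go further than the appendix does and is not needed.
2. Reconcile Section 3.2 with Section 6.1.4.4: state which criterion governs ORR and the 15-patient interim count, and report ORR under the other criterion as well.

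The cost is wording in Appendix 4, Section 3.2 or 6.1.4.4, and Section 7.2. No extra scans follow, because the derivation uses whatever imaging is done. The downside is a slightly lower iRECIST ORR and an endpoint label that can differ from the label the site uses for management.
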